2. Creatinine, bilirubin, ALT or AST once monthly prior to start of each cycle.
3. Bone marrow aspirate and/or biopsy to confirm response, to be performed after cycle 2 then every 3 cycles for the first year, then every 6 cycles thereafter.
All bone marrows will be performed by the registering center, not in the local MD office.
4. Conventional cytogenetics to be performed after cycle 2 then every 3 cycles for the first year, then every 6 cycles thereafter
5. Documentation of frequency of transfusions (PRBC and Platelets) prior to start of each cycle.
6. Documentation in the medical record of any grade 3 or higher possibly, probably, definitely related adverse events that have occurred prior to start of each cycle. For guidelines on SAE Reporting and AE entry for Case Report

Forms (CRF), please refer to Appendix A (for MD Anderson) and Appendix G (for Participating Institutions).

7. Documentation of any prior administration of growth factors and ESA prior to start of each cycle

Table 2: Evaluation

Test	Pre-treatment	During treatment
CBC, differential platelet count	within 14 days of treatment start	Monthly prior to start of each cycle (+/- 7 days)
Creatinine, bilirubin, ALT or AST	within 14 days of treatment start	Monthly prior to start of each cycle (+/- 7 days)
Bone marrow aspirate	Within 6 weeks prior to study entry	after cycle 2 then prior to every 3 cycles for the first year, then prior to every 6 cycles thereafter
Cytogenetics	Within 3 months prior to study entry	after cycle 2 then prior to every 3 cycles for the first year, then prior to every 6 cycles thereafter
Serum or urine pregnancy test for woman of childbearing potential	within 7 days of treatment start	
Transfusion history documented	Prior to study entry	Prior to start of each cycle
Growth factors and ESA documentation	Prior to study entry	Prior to start of each cycle

Follow-Up

Following completion of active treatment and while still on study, patients will be followed for survival approximately every 6 to 12 months for up to 5 years. This follow up can either be done as a visit to the study doctor's clinic or via telephone call to the patient.

Chemotherapy administration

If the study doctor decides it is acceptable, enrolled subjects may be allowed to receive treatment from their local cancer doctor following cycle 1 (appendix B). However, enrolled subjects will have to return to the study doctor's clinic at least every 3 cycles for study visits.

Supportive care

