The response criteria recommended by the MDS International Working Group 2006.

Responses must be verified, documented, and signed in the local medical record by the local PI. (Patients are considered non evaluable if they have received less than 2 courses of treatment, unless there is clear disease progression.)

Definitions:

Complete Response (CR):

Bone marrow: $\leq 5\%$ myeloblasts with normal maturation of all cell lines; persistent dysplasia will be noted

Peripheral blood:

Hgb ≥ 11 g/dL

Platelets $\geq 100 \times 10^9/L$

Neutrophils $\geq 1.0 \times 10^9/L$

Blasts 0%

Partial response (PR):

All CR criteria if abnormal before treatment except: bone marrow blasts decreased by $\geq 50\%$ over pretreatment but still $> 5\%$

Marrow CR:

Blasts \leq 5% and decrease by \geq 50% from baseline (baseline blasts should be above 5% to be eligible for marrow CR)

Hematologic Improvement (HI): (responses must last at least 8 weeks)

Erythroid response [HI-E; (if pretreatment Hgb $<$ 11 g/dL)]; Hgb increase by \geq 1.5 g/dL; Relevant reduction of units of RBC transfusions by an absolute number of at least 4 RBC transfusions/8 weeks compared with the pretreatment transfusion number in the previous 8 weeks. Only RBC transfusions given for a Hgb of \leq 9.0 g/dL pretreatment will count in the RBC transfusion response evaluation.

Platelet response [HI-P; ((if pretreatment Platelet count $<$ $100 \times 10^9 /L$)]: Absolute increase of $\geq 30 \times 10^9 /L$ for patients starting with $> 20 \times 10^9 /L$ platelets, or increase from $< 20 \times 10^9 /L$ to $> 20 \times 10^9 /L$ and by at least 100%.

Neutrophil response [HI-N; (pretreatment, ANC $< 1.0 \times 10^9 /L$)]: At least 100% increase and an absolute increase $> 0.5 \times 10^9 /L$

Progression/Relapse after hematological improvement: ≥ 1 of the following: $\geq 50\%$ decrement from maximum response levels in granulocytes or platelets; \downarrow in Hgb by ≥ 1.5 g/dL; transfusion dependence

Stable Disease: Not satisfying criteria for Complete Remission, Partial Response, Marrow CR, Hematologic Improvement or Progression/Relapse.

IX. REPORTING REQUIREMENTS

All adverse and serious adverse events will be recorded and reported according to the Leukemia-Specific Adverse Events (appendix A). The MD Anderson Leukemia

Department will report SAEs in accordance with MD Anderson IRB policies and procedures and Appendix A of the protocol.

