Participating Multicenter Institutions SAE requirements will be followed as written in the Data Quality Management Plan.

X. Randomization

The Department of Biostatistics at MD Anderson will provide and maintain a website (“Clinical Trial Conduct”: <https://biostatistics.mdanderson.org/ClinicalTrialConduct/>) for patients enrolled on this study. The Clinical Trial Conduct website resides on a secure server, and access is gained through usernames and passwords provided to personnel responsible for enrolling patients and updating patient data. The website is accessed through a browser using secure socket layer (SSL) technology. Personnel responsible for enrolling patients on trials, which includes the principal investigator(s), research nurse(s), and data coordinator(s), will be trained by members of the Department of Biostatistics in the use of the trial website; the importance of timely updating of follow-up times and recording of events will be emphasized in training.

XI. Data Safety Monitoring

A data safety monitoring board (DSMB) at MD Anderson will monitor the trial for the safety.

XII. STATISTICAL CONSIDERATIONS

General Description

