Patients will be randomized using a Bayesian adaptive algorithm. Patients will be randomized fairly among the three arms at the start of the trial (for the first 30 patients), that is, 10 patients per arm. Thereafter, as the trial progresses and data accrue, the randomization will become unbalanced in favor of the treatment that, on average, has better results in terms of event free survival. Therefore, each successive patient is more likely to receive the treatment with better results, on average. A minimum of 30 and a maximum of 150 patients will be accrued. There will be 12 months follow up after the last patient is accrued with an anticipated accrual rate of 5 patients per month.

Denote the event free survival for the patients in the three arms (DAC; AZA3; AZA5) as T_i for $i=1,2,3$. Assume the T_i is independent exponential with median μ_i . And each μ_i independently follows an inverse gamma distribution with parameter $\alpha=2.05$, $\beta=7.34$. The parameters were chosen to set the mean of the prior equal to 7 (the historical median EFS in months) and a variance of 1000. For each patient, the randomization probability for treatment arm i will be based on the posterior probability that it has the largest median EFS. For example, for arm 1, the posterior probability is $\pi_1=\Pr(\mu_1 > \mu_i)$ for $i=2,3$. In order to avoid aggressively favoring one arm too early in a large trial, instead of

assigning patients with posterior probability, we use its square root transformation as in the following formula to assign patients:

$$Aa = \frac{\sqrt{\pi_1}}{\sqrt{\pi_1} + \sqrt{\pi_2} + \sqrt{\pi_3}}, \text{ where } Aa \text{ is the probability of assigning patients to arm 1, } \pi_1 \text{ is}$$

the posterior probability that arm 1 is superior, etc.

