	Pr (stopped early)	0.806	0.814	0.028
3	True Median EFS	3	3	3
	# of patients treated	10.5	10.5	10.5
	Pr(selected)	0.046	0.043	0.045
	Pr(selected early)	0.001	0.001	0.001
	Pr (stopped early)	0.779	0.779	0.777
4	True Median EFS	7	9	14
	# of patients treated	23.6	36.2	57.4
	Pr(selected)	0.003	0.013	0.882
	Pr(selected early)	0.0002	0.003	0.217
	Pr (stopped early)	0.921	0.686	0.0162
5	True Median EFS	7	12	12
	# of patients treated	23.1	56.6	55.6
	Pr(selected)	0.001	0.242	0.235
	Pr(selected early)	0.0002	0.04	0.036
	Pr (stopped early)	0.877	0.12	0.13

6	True Median EFS	4	7	12
	# of patients treated	13.3	29.5	45.3
	Pr(selected)	0.001	0.014	0.883
	Pr(selected early)	0	0.002	0.357
	Pr (stopped early)	0.994	0.866	0.036
7	True Median EFS	4	7	10
	# of patients treated	13.9	34.1	48.1
	Pr(selected)	0.001	0.039	0.757
	Pr(selected early)	0	0.004	0.194
	Pr (stopped early)	0.987	0.661	0.083

Toxicity Monitoring

Evidence of toxicity will be monitored closely for all patients. As expected, there will be 150 transfusion-dependent patients enrolled which includes the 120 patients initially recruited and another 30 patients who have changed from transfusion independence to dependence. With 10 patients fairly randomized to each arm, there will be at most 120 patients being adaptively assigned to any of the three arms. Taking the initial 10 patients assigning to each arm, the maximum number of patient per treatment arm will be 130. For each treatment, treatment will be terminated if $\Pr(\theta_E > 0.2 | \text{data}) > 0.9$, where θ_E is the proportion of any grade 3 or higher treatment related non-hematologic toxicities. It is assumed to follow a non-informative prior of Beta (0.4, 1.6) That is, the trial will be terminated if at any time during the study, there is a more than 90% chance that the average rate of grade 3 or greater treatment related non-hematologic toxicity is more than 20%. Patients will be monitored by a cohort size of 10 according to the following stopping boundaries for toxicity. The design software Multc Lean Desktop (version 2.1) developed by the Department of Biostatistics at M. D. Anderson Cancer

Center (MDACC) was used to generate the futility/toxicity stopping boundaries and the OC table.

Table 4: stopping boundaries for toxicity

Number of patients evaluated	Stop the trial if there are this many treatment related toxicities
10	5-10
20	7-20
30	10-30
40	12-40
50	15-50
60	17-60
70	19-70
80	21-80
90	24-90
100	26-100
110	28-110
120	30-120

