Appendix A

Appendix Subtitle:

Leukemia-specific Adverse Event Recording and Reporting Guidelines

These guidelines serve to bring the Department of Leukemia in compliance with the institutional policy on Reporting of Serious Adverse Events-definition of expected AE- "All clinical protocols should include a list of the expected and anticipated events or hospitalizations relating to the study treatment" and Guideline for Good Clinical Practice 4.11.1 "All serious adverse events (SAEs) should be reported immediately to the sponsor except for those SAEs that the protocol or other document (e.g., Investigator's Brochure) identifies as not needing immediate reporting".

Adverse event is any untoward medical occurrence that may present during treatment with a pharmaceutical product but which does not necessarily have a causal relationship with this treatment.

Adverse drug reaction is a response to a drug which is noxious and unintended and which occurs at doses normally used in man for prophylaxis, diagnosis, or therapy of disease or for the modification of physiologic function.

Assessing causal connections between agents and disease is fundamental to the understanding of adverse drug reactions. In general, a drug may be considered a contributory cause of an adverse event if, had the drug not been administered, 1) the event would not have happened at all, 2) the event would have occurred later than it actually did, or 3) the event would have been less severe.

Adverse Events (AEs) will be evaluated according to current CTC version in each protocol. Only unexpected AEs will be recorded in the Case Report Form (CRF).

Expected events during leukemia therapy are:

1. *Myelosuppression related events (due to disease or leukemia therapy)*
 - a. *febrile or infection episodes not requiring management in the intensive care unit*
 - b. *epistaxis or bleeding except for catastrophic CNS or pulmonary hemorrhage*
 - c. *anemia, neutropenia, lymphopenia, thrombocytopenia, leukopenia, leukocytosis*
2. *Disease related events*
 - a. *symptoms associated with anemia*
 - i. *fatigue*
 - ii. *weakness*
 - iii. *shortness of breath*
 - b. *electrolyte abnormalities (sodium, potassium, bicarbonate, CO₂, magnesium)*
 - c. *chemistry abnormalities (LDH, phosphorus, calcium, BUN, protein, albumin, uric acid, alkaline phosphatase, glucose)*
 - d. *coagulation abnormalities*
 - e. *disease specific therapy (induction, maintenance, salvage, or stem cell therapy)*

- f. alopecia

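### Tables 5 and 8 give toxicity stop probabilities for one arm run to 120 or 80 patients without saying so, and the text conflicts on whether a crossing ends one treatment or the trial

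*Combined protocol and SAP*

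**What the plan says.** **The rule.** Section XII, Toxicity Monitoring, counts grade 3 or higher treatment-related non-hematologic toxicities, with a Beta(0.4, 1.6) prior and a look every 10 patients. The criterion is a posterior probability above 0.90 (Part I) or 0.88 (Part II) that the rate exceeds 20%. Boundaries are in Table 4 (looks at 10 to 120) and Table 7 (looks at 10 to 80). Stop probabilities are in Tables 5 and 8, with no arm size or number of arms attached.

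**The unit.** Part I opens with "For each treatment, treatment will be terminated if" the criterion is met. It then continues: "That is, the trial will be terminated if at any time during the study, there is a more than 90% chance". Part II has the same pair of statements with 88%. The headings of Tables 4, 5, 7 and 8 all speak of stopping the trial.

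**The sample size.** For Part I, "A minimum of 30 and a maximum of 150 patients will be accrued"; Part II is capped at 120. The per-arm maxima are given as 130 and 90.

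**The record.** Section IX says "All adverse and serious adverse events will be recorded and reported according to the Leukemia-Specific Adverse Events (appendix A"). Appendix A says "Only unexpected AEs will be recorded in the Case Report Form (CRF"). Section VI, During therapy, item 6 requires "Documentation in the medical record of any grade 3 or higher possibly, probably, definitely related adverse events" before each cycle. For CRF entry it sends the lead center to Appendix A and participating institutions to Appendix G. For the latter, Section IX adds: "Participating Multicenter Institutions SAE requirements will be followed as written in the Data Quality Management Plan".

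**The concern.** A monitoring board needs to know how likely the rule is to act on an arm with too much toxicity, and what happens when it acts. Read at face value, Tables 5 and 8 promise a 0.94 or 0.88 chance of stopping at a 30% rate. If those figures belong to arm sizes that the design seldom reaches, the board has no stated figure for the arms it will actually see. If a crossing ends the whole trial, three drug arms each get a chance to trigger it, and the stated chance of stopping at an acceptable rate is too low.

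The second, lesser question is where the count comes from. Appendix A's expected list includes events attributed to disease or leukemia therapy: infection not needing intensive care, and bleeding other than catastrophic CNS or pulmonary hemorrhage. If the toxicity count or the secondary safety endpoint were drawn from a CRF that omits expected events, some qualifying events could be left out.

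**Working it through.** **1. Reproduce the boundaries.** At each look n, take the smallest x for which Pr(Beta(0.4 + x, 1.6 + n − x) > 0.20) exceeds 0.90 (Part I) or 0.88 (Part II). This gives 5, 7, 10, 12, 15, 17, 19, 21, 24, 26, 28, 30 at n = 10 to 120, and 4, 7, 9, 12, 14, 17, 19, 21 at n = 10 to 80. All 12 entries in Table 4 and all 8 in Table 7 agree.

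**2. Reproduce the stop probabilities.** Exact sequential binomial calculation for one arm: add Binomial(10, p) toxicities per look, remove the probability at or above the boundary, and carry the rest forward.

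| True rate | Part I, one arm to 120 | Table 5 | Part II, one arm to 80 | Table 8 |
|---|---|---|---|---|
| 0.15 | 0.042 | 0.04 | 0.080 | 0.08 |
| 0.20 | 0.250 | 0.25 | 0.281 | 0.28 |
| 0.25 | 0.676 | 0.68 | 0.616 | 0.62 |
| 0.30 | 0.942 | 0.94 | 0.881 | 0.88 |

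Taking any of three arms to the last look gives 0.121/0.578/0.966/1.000 and 0.222/0.628/0.944/0.998, which match neither table. So the tables describe one monitored group run to the last listed look.

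**3. Can arms get that far?** Two arms at 120 need 240 patients against a cap of 150. Two at 80 need 160 against 120. At most one arm per part can reach the look. If one Part I arm reaches 120, the other two share 150 − 120 = 30; each already has 10 from the equal phase, so neither exceeds 20. The largest mean arm sizes are 57.4 (Table 3, scenario 4) and 42.5 (Table 6, scenario 5). With equal efficacy at the historical median (scenario 1) they are 40.1–40.6 in Part I and 28.6–28.9 per drug arm in Part II.

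**4. The same calculation ended earlier (one arm).**

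| Arm ends at | Part I, 15% | Part I, 25% | Part I, 30% | Part II, 15% | Part II, 25% | Part II, 30% |
|---|---|---|---|---|---|---|
| 10 | 0.010 | 0.078 | 0.150 | 0.050 | 0.224 | 0.350 |
| 20 | 0.027 | 0.229 | 0.408 | 0.060 | 0.306 | 0.485 |
| 30 | 0.030 | 0.284 | 0.504 | 0.072 | 0.417 | 0.642 |
| 40 | 0.035 | 0.368 | 0.630 | 0.074 | 0.455 | 0.698 |
| 60 | 0.037 | 0.453 | 0.750 | 0.078 | 0.538 | 0.802 |
| Stated | 0.04 | 0.68 | 0.94 | 0.08 | 0.62 | 0.88 |

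**5. If any one arm crossing ends the trial.** With three independent drug arms of equal size, the stop probability is 1 − (1 − p)³, where p is the per-arm value.

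- All at 15%, Part I, 40 per arm: 1 − (1 − 0.035)³ = 0.10 (stated 0.04).
- All at 15%, Part II, 20 per arm: 1 − (1 − 0.060)³ = 0.17; 30 per arm: 1 − (1 − 0.072)³ = 0.20 (stated 0.08).
- All at 30%, Part I, 40 per arm: 1 − (1 − 0.630)³ = 0.95 (stated 0.94), so that row hardly moves.

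**6. The record.** There is no arithmetic here. Related grade 3+ events are in the medical record (Section VI). Hospitalizations for expected events are in the SAE log, and grade 3–4 chemistry values do go in the CRF (both Appendix A). No text available for this review says which record feeds the toxicity count, or whether related infection and bleeding, listed under a myelosuppression heading, count as non-hematologic.

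**The case against.** **This is labelling.** The tables are correct, each sits directly after its boundary table, and the per-arm maximum is stated just before. A careful statistician can infer the basis. That is true, but a board member should not have to rebuild the calculation to learn that 0.94 belongs to an arm of 120.

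**The any-arm model is written nowhere.** Correct. It is one reading of the restatement that the trial ends, and a pooled count would be another. A pooled group followed to 120 or 80 would give the same figures as one arm; the per-arm basis is inferred from the opening clause and the per-arm maxima. The any-arm figures show what hangs on the wording. They are not a claim about what was intended.

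**Fixed sizes are not performance.** This stands. Allocation is adaptive, arms vary around the means, and a small arm exposes fewer patients. A reader might infer from 0.63 that 37% of arms at a 30% rate go undetected; the documents give mean sizes, not a distribution, so no such share follows.

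**There are other protections.** Discontinuation for side effects is an EFS event, so a toxic arm may also lose allocation or be dropped. A DSMB monitors safety, and unacceptable toxicity is a reason for withdrawal. These reduce the consequences but do not make the tables describe the rule.

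**The CRF point is conditional.** This also stands. A reader might infer that Appendix A makes the rule undercount. The documents do not support that: no passage ties the rule to the CRF, related grade 3+ events are kept in the medical record, and the overlap with a non-hematologic count is not established. Appendix G and the Data Quality Management Plan are not in the text available for this review, so nothing is claimed about participating sites.

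**Conclusion.** The main point holds. Tables 5 and 8 are not miscalculated; their basis is unstated, and at most one arm per part can reach it. Per arm, at a size near the equal-efficacy mean, the chance of stopping at a 30% rate is about two thirds of what Table 5 states (0.630/0.94 = 0.67) and about three quarters of what Table 8 states (0.642/0.88 = 0.73). At 25% it is 0.37 against 0.68, and 0.42 against 0.62. The 15% row is essentially unaffected per arm, but on the any-arm reading it more than doubles.

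The passages on what a crossing ends contradict each other and must be reconciled; which unit is right is for the sponsor to say. The figures assume fixed arm sizes, every patient evaluable at each look and, for the any-arm reading, independent arms of equal size.

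The CRF point is secondary: a possible omission at the lead center if the CRF is the source, with no demonstrated loss and no size given by the documents.

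**What to change.** 1. Label Tables 5 and 8 as one arm followed to 120 or 80 patients, and add per-arm rows at 10, 20, 30, 40 and 60 patients.
2. Reconcile the two statements of what is terminated, in both Toxicity Monitoring sections and in the headings of Tables 4, 5, 7 and 8. Give stop probabilities for the unit that results. The boundaries stay unchanged.
3. In Appendix A and Section IX, require CRF entry of all grade 3+ treatment-related non-hematologic AEs, expected or not. In Section XII, name that record as the source of the count and state whether related infection and bleeding count as non-hematologic. Make the same check of Appendix G for participating sites.

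The cost is some extra CRF entry of events already documented in the medical record, plus longer tables with less favourable stated figures.

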Appendix B

mm/dd/yyyy

Dear Doctor,

(Name) is a mutual patient of ours who has been enrolled on Protocol 2014-0112: Phase II Randomized Study of Lower Doses of Decitabine versus Azacitidine (3 day schedule) versus Azacitidine (5 day schedule) in MDS Patients with Low and Intermediate-1 Risk Disease Transfusion-Dependent versus Best Supportive Care (BSC) in MDS Patients with Low and Intermediate-1 Risk Disease Transfusion-Independent at M.D. Anderson Cancer Center in Houston, TX from _____ to present.

The patient was randomized to treatment arm with _____. The patient's current treatment course is course ___ of this regimen. Following one cycle performed here at MD Anderson Cancer Center, this study requires enrolled patients to return to be seen in our clinic at least every three months for study visits.

(Name) would like to come home for the _____ treatment and interim tests, however, in order for us to support follow up at home we will need the following:

1. A confirmation of your center feasibility to perform required testing of CBC with differential and platelets at least monthly and serum bilirubin, creatinine, SGPT or SGOT once per month. More frequent testing may be performed at your discretion.
2. A faxed copy of the documented dictated or handwritten findings of visits as soon as they became available including the above monthly laboratory results, weekly progress notes/clinic notes, physician order for _____ administration, _____ medication administration records, hospital admission summary, hospital discharge summary.
3. A copy of your lab's certification.

If the above protocol requirements are not feasible to be performed at your center, please let us know so that we may arrange for other plans.

If you agree, we would ask you to sign and return this letter as confirmation that we will receive by fax, a copy of all labs, medication administration records, and a copy of the dictated or handwritten clinic visit notes regarding assessments.

The study requires enrolled patients to return to be seen in our clinic at least every three months for study visits.

A follow up visit at MDACC, for evaluation of response and additional testing is scheduled for:

We have included a copy of the abstract for your convenience.

By signing below, I agree to perform all tests and evaluations as noted above, and fax all documentation to [contact].

Please fax all the above protocol documents as soon as possible to [contact].
